8.2.4. Effectiveness Analysis

8.2.4.1. Clinical Response

In the clinical response analysis set, the number and proportion of patients with each clinical response will be calculated. In addition, the number and proportion (response rate) of responders and the 95% CI of response rate will be calculated in the clinical efficacy analysis set excluding patients with indeterminate response. Similar calculations will be tabulated by diagnosis (including by detailed diagnostic name of anaerobic infection), by maximum number of daily doses, and by the occurrence of central nervous system disorder. The response rate can be calculated by the following formula:

Clinical response rate (%) = (Number of patients with “effective”/ Number of clinically-evaluable patients excluding “indeterminate”) $\times 100$.

If the clinical efficacy analysis set includes patients with inconsistent clinical efficacies, the response rate will be calculated by subtracting those patients from the denominator, as in the case where the set includes “indeterminate” patients.

In addition, the number and proportion (clinical response rate) of responders and the 95% CI of response rate for each pathogenic organism/strain will also be tabulated by diagnosis.

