7.3.6. Effectiveness evaluation

(1) Clinical response

The clinical response of this drug should be evaluated comprehensively at the completion of the observation period, and the results should be recorded.

If this drug is administered continuously for more than 8 weeks, the clinical response should be evaluated comprehensively at Week 8.

- Effective
- Not effective
- Indeterminate (the reason should be recorded.)

The assessment criteria shall be as follows:

Table 2. Assessment criteria for [anaerobic infection] / [infectious enterocolitis (including pseudomembranous colitis)]

Assessment	Definition
Effective	Clinical symptoms accompanying the infection observed at the initiation of treatment with this drug has improved at the time of assessment, and treatment with other antibacterial drugs after the time of assessment is determined not necessary.
Not effective	"Effective" criteria are not met.
Indeterminate	Clinical response is difficult to evaluate.

Table 3. Assessment criteria for [amebic dysentery]

Assessment	Definition
Effective	Clinical symptoms accompanying the infection observed at the initiation of treatment with this drug has improved at the time of assessment, and treatment with other antibacterial drugs other than antiamebic agents (paromomycin, etc.) after the time of assessment is determined not necessary.
Not effective	"Effective" criteria are not met.
Indeterminate	Clinical response is difficult to evaluate.

Any clinically problematic finding compared to the initiation of treatment should be recorded in details in the AE column.

(2) Rationale for clinical response assessment

The rationale for the clinical response assessment ("Effective" or "Not effective"), on the disease for which this drug is used, should be recorded.

[Anaerobic infection]

General clinical findings, body temperature, WBC count, CRP level, imaging, and others

[Infectious enterocolitis (including pseudomembranous colitis)]

General clinical findings, Clostridium difficile TOXIN test, frequency of diarrhea, body temperature, abdominal pain, and others

[Amebic dysentery]

General clinical findings, ameba test, frequency of diarrhea, body temperature, abdominal pain, and others

(3) Microbiological response assessment

Microbiological response at the completion of observation period compared to prior to the initiation of treatment with this drug should be assessed, and the results should be recorded.

Table 4. Assessment criteria for microbiological response

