7.7. Data analysis

The details of methods of analysis on data collected in this study shall be described in the statistical analysis plan (SAP) to be separately prepared.

- Definition of analysis set

The safety analysis set shall include patients for whom the registration in this study and administration of this drug have been confirmed.

Two analysis sets, which are clinically-evaluable analysis set and microbiological analysis set shall be defined as the effectiveness analysis set. The clinically-evaluable analysis set includes patients who were confirmed to conduct the clinical evaluation in the safety analysis set. The microbiological analysis set includes patients for whom microbiological response was assessed in the clinically-evaluable analysis set.

- Methods of analysis

(1) Analysis for safety evaluation

The incidence of adverse reactions will be calculated for each event. Also, the factors affecting the occurrence of adverse reaction will be evaluated as necessary.

(2) Analysis for effectiveness evaluation

The clinical response rate in terms of the clinical effectiveness will be set as the primary effectiveness endpoint. The number of patients with "effective" and its proportion (clinical response rate) among the clinically-evaluable analysis set, and its 95% confidence interval will be calculated. The number of patients with eradication or presumed eradication, and its proportion (eradication rate) among the microbiological analysis set, and its 95% confidence interval will be calculated. The clinical response rate for each disease and its 95% confidence interval, and the eradication rate and its 95% confidence interval will be calculated. Also, an exploratory analysis on the factors affecting the effectiveness will be performed as necessary.

$$\text{Clinical response rate (\%)} = \frac{\text{Number of patients with "effective"} }{\text{Number of clinically-evaluable patients excluding "indeterminate"} } \times 100$$

$$\text{Eradication rate (\%)} = \frac{\text{Number of patients with "eradication" + "presumed eradication"} }{\text{Number of patients in the microbiological analysis set excluding "indeterminate"} } \times 100$$

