Detailed methodology for summary and statistical analyses of data collected in this study will be documented in a SAP, which will be dated, filed and maintained by the Sponsor. The SAP may modify the plans outlined in the protocol; any major modifications of primary endpoint definitions or their analyses would be reflected in a protocol amendment.

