6.2. Effectiveness Endpoints

6.2.1. Clinical Response

At the end of observation period or at the time of discontinuation, clinical response will be assessed by the physician from a comprehensive perspective according to the criteria below. If this drug is administered continuously for more than 8 weeks, the clinical response should be evaluated comprehensively at Week 8. The definitions are as follows.

- Reason for the use: anaerobic infection:
 - Effective: Clinical symptoms accompanying the infection observed at the initiation of treatment with this drug has improved at the time of assessment, and treatment

with other antibacterial drugs after the time of assessment is determined not necessary.

- Not effective: "Effective" criteria are not met.
- Indeterminate: Clinical response is difficult to evaluate.

- Reason for the use: infectious enterocolitis (incl. pseudomembranous colitis):
 - Effective: Clinical symptoms accompanying the infection observed at the initiation of treatment with this drug has improved at the time of assessment, and treatment with other antibacterial drugs after the time of assessment is determined not necessary.
 - Not effective: "Effective" criteria are not met.
 - Indeterminate: Clinical response is difficult to evaluate.
- Reason for the use: amebic dysentery:
 - Effective: Clinical symptoms accompanying the infection observed at the initiation of treatment with this drug has improved at the time of assessment, and treatment with other antibacterial drugs other than antiamebic agents (paromomycin, etc.) after the time of assessment is determined not necessary.
 - Not effective: "Effective" criteria are not met.
 - Indeterminate: Clinical response is difficult to evaluate.

In this Study, clinical response may be evaluated for each diagnosis. If the same patient have multiple diagnoses under investigation with different clinical response, the patient will be handled as a “inconsistent clinical response” case for overall clinical response evaluation is difficult.

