8.2.4.4. Subgroup Analysis

For each factor specified in Section 5.4, subgroup analysis on clinical response and microbiological response will be performed based on risk ratio and risk difference. Similar calculations will be tabulated by disease category (anaerobic infection, infectious enterocolitis, amebic dysentery).

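### Patients with differing ratings across target diagnoses leave the clinical response denominator, including those with a recorded failure, and no planned analysis gives the overall rate with them kept in

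*SAP*

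**What the plan says.** Protocol 7.7 makes the clinical response rate the primary effectiveness endpoint. Its denominator is given as "Number of clinically-evaluable patients excluding" the indeterminate category. The formula printed in SAP 8.2.4.1 has the same denominator.

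SAP 6.2.1 adds a patient-level class. It applies "If the same patient have multiple diagnoses under investigation with different clinical response", and such a patient is handled as an inconsistent "case for overall clinical response evaluation is difficult". SAP 8.2.4.1 then says that, if the set includes such patients, "the response rate will be calculated by subtracting those patients from the denominator", as is done for indeterminate patients.

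Two other statements in Protocol 7.7 and 7.3.6 matter here. The SAP may modify the protocol's plans, but "any major modifications of primary endpoint definitions or their analyses would be reflected in a protocol amendment". And the protocol defines the indeterminate rating by the words "Clinical response is difficult to evaluate".

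On reporting, SAP 8.2.4.1 plans that "the number and proportion of patients with each clinical response will be calculated", with rates by diagnosis, and SAP 9 plans a listing of clinical response. SAP 5.4 allows combined-diagnosis categories. For the factors in 5.4, SAP 8.2.4.4 says that "subgroup analysis on clinical response and microbiological response will be performed based on risk ratio and risk difference".

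**The concern.** A difference in rating can arise in three ways: effective with not effective, not effective with indeterminate, or effective with indeterminate. The SAP treats all three alike.

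The last is close to the protocol's idea of an indeterminate patient. The first two are not, because in each at least one target infection was assessed and rated a failure. Removing those patients takes recorded failures out of the denominator because of their outcome. It also leaves the printed formula and the operating rule describing different denominators for the same endpoint.

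What is at stake is how the overall rate is read. Protocol 7.5.2 intends the study to show whether effectiveness in practice is similar to the clinical study, overall and by major indication. A reader making that comparison would want the rate with these failures kept in, and no planned analysis provides it.

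**Working it through.** **A figure in the plan to reproduce.** The documents give no figure for the effect of this exclusion. The only related number is the sample size basis: the chance of seeing at least one case of a reaction with 3% incidence in 100 patients is 1 − 0.97^100 = 0.952, which matches the stated 95%. It confirms the planned size of about 100 and says nothing about this rule.

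**Notation.** Let x be the number effective and n the number effective or not effective, both leaving out inconsistent patients. Let k be the number of inconsistent patients with at least one not effective rating.

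- Planned rate: x/n
- All k counted not effective: x/(n + k)
- All k counted effective: (x + k)/(n + k)

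Effective/indeterminate patients, if classed as indeterminate, stay out of all three and do not change the planned rate.

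**Order of the three rates.** x/(n + k) ≤ x/n, because the denominator grows. Also x/n ≤ (x + k)/(n + k), because this reduces to xk ≤ nk, which holds since x ≤ n. So the planned rate always lies between the two bounds. When response is high it lies nearer the upper one.

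**Illustration.** The counts are assumptions: x = 76 effective and 14 not effective, so n = 90. Intervals are exact (Clopper-Pearson), as SAP 8.1.3 specifies an exact method.

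| Case | All k not effective | Planned | All k effective |
|---|---|---|---|
| k = 2 | 76/92 = 82.6% (73.3 to 89.7) | 76/90 = 84.4% (75.3 to 91.2) | 78/92 = 84.8% (75.8 to 91.4) |
| k = 5 | 76/95 = 80.0% (70.5 to 87.5) | 76/90 = 84.4% (75.3 to 91.2) | 81/95 = 85.3% (76.5 to 91.7) |

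The planned rate exceeds the lower bound by 84.4 − 82.6 = 1.8 points for k = 2 and by 84.4 − 80.0 = 4.4 points for k = 5. It is below the upper bound by 0.4 and 0.9 points (rounded rates).

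**Range.** With n + k = 100 and a planned rate near 80%:

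- k = 2: 78/98 = 79.6%, bounds 78.0% and 80.0%
- k = 5: 76/95 = 80.0%, bounds 76.0% and 81.0%
- k = 10: 72/90 = 80.0%, bounds 72.0% and 82.0%

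The gap to the lower bound is 1.6, 4.0 and 8.0 points. Nothing in the documents says which k is likely.

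**Combined-diagnosis comparison (illustration only).** SAP Appendix 2 gives anaerobic infection plus infectious enterocolitis against anaerobic infection as an example categorization. If the same rule is applied within that category, it can remove patients on one side only. Assume 10 combined patients (7 effective, 1 not effective, 2 effective/not effective) against 68/80 = 85.0%. The Wald intervals on the log scale are my choice, since the SAP names no risk-ratio interval method.

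- Planned: 7/8 = 87.5%, risk ratio 1.03 (0.78 to 1.36)
- Both counted not effective: 7/10 = 70.0%, risk ratio 0.82 (0.54 to 1.25)
- Both counted effective: 9/10 = 90.0%, risk ratio 1.06 (0.84 to 1.33)

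The intervals overlap widely.

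**The case against.** The case for leaving the rule alone is substantial.

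- **It is disclosed and planned.** The exclusion stands directly below the formula. It entered the SAP in version 2.0 of August 2016, before registration closed in March 2017 and before database release was in preparation. This stands. A reader might infer a concealed or after-the-fact choice, and the documents do not support that.
- **It has a stated reason.** SAP 6.2.1 says an overall evaluation is difficult, which echoes the protocol's ground for indeterminate. This supports a separate category. It does not explain why a patient with a recorded failure should leave the rate without any check of the effect.
- **Simple bounds need only a total.** Counting every inconsistent patient as not effective, then as effective, gives valid outer bounds from one count, which the table of each clinical response may well show. This stands. A reader might infer that no bounds can be formed without a breakdown by pair of ratings, and that is not so. The split proposed below only avoids counting effective/indeterminate patients as failures.
- **Other outputs help.** By-diagnosis rates are planned, and a listing that shows each diagnosis's rating would let a reader find a few such patients among about 100. This reduces the weight of the point. Neither output is an overall rate with these patients kept in.
- **The size is hypothetical.** No counts are given. For two patients the shift is under 2 points, inside an interval about 16 points wide (91.2 − 75.3 = 15.9). SAP 4.1 calls the tests exploratory and SAP 4.2 has no decision rule. This also stands.

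**Conclusion.** The point holds as one about reporting and sensitivity analysis. The SAP removes patients with a recorded not effective rating from the denominator of the primary effectiveness rate, while both printed formulas exclude only indeterminate patients. The resulting rate is higher than if those patients were kept as not effective. Under the assumed 76 and 14, the excess is 1.8 points for two such patients and 4.4 points for five. The actual number is not in the documents and may be zero. The effect is on interpretation only.

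Two stronger readings are not supported. A reader might infer a breach of the protocol, because its one amendment changed only dates. But Protocol 7.7 lets the SAP modify its plans and asks for an amendment only for major modifications of the primary endpoint or its analysis. Whether this change is major is a judgement. A reader might also infer that the planned rate can lie above both bounds. That happens only if the upper row is made to score not effective/indeterminate patients as not effective, in which case it is no longer a best case. Against the simple bounds, the planned rate always lies between them.

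**What to change.** In SAP 8.2.4.1, with the matching definition in 6.2.1:

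1. Report the number of inconsistent patients, split by whether any target diagnosis was rated not effective.
2. Class effective/indeterminate patients as indeterminate. This leaves the planned rate unchanged.
3. Add two sensitivity rates with exact 95% intervals, for the overall rate and for any combined-diagnosis category: (a) every patient with a not effective rating counted as not effective; (b) the same patients counted as effective. Row (b) is a bound and not a proposed scoring rule.
4. Make the SAP formula and the sentence below it state the same denominator.

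The planned rate may stay primary, and the by-diagnosis rates stay as they are.

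The cost is a few sentences, one count and two table rows, from ratings already collected. The rate in row (a) may look slightly less favourable. If no inconsistent patient occurs, the rows can be omitted.

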7.5. Study size

7.5.1. Planned sample size

100 patients (for safety analysis)

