7.5.2. Rationale for sample size

The target sample size was set to be 100 patients, which should enable to detect, at 95% probability, an adverse reaction of which the true incidence rate is 3% in reference to adverse reaction of the least incidence in a clinical study of this drug (Study A6831005). This sample size should enable to confirm whether the types and incidence of adverse reaction related to this

drug used for diseases other than intra-abdominal infection, and pelvic inflammatory disease and other related diseases (hereinafter referred to as "PID") that were targeted in the clinical study would be similar to those occurred in Study A6831005.

Events specified as important identified risks or important potential risks in the Risk Management Plan (RMP) may not have a high incidence, and thus, may not detect sufficient information only from the drug use investigation; nonetheless, such an event collected in the drug use investigation should be investigated within the framework of the drug use investigation. Moreover, these events should also be monitored through the routine pharmacovigilance activities.

The sample size of 100 patients are expected to enable accumulating data on the number of patients at the level similar to the clinical study in terms of clinical response rate of this drug for diseases other than intra-abdominal infection and PID that were targeted in the clinical study and also in terms of clinical response rate in subgroup analysis by each major indication; which should enable verification whether the effectiveness under actual clinical settings is similar to the results of the clinical study.

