10.2. Appendix 2: Example of Categorizations for Risk Ratio Analysis

Exploratory categorization factors might be added to the set below. If an additional factor is one that categorized by absent or present, “absent” will be chosen as the reference.

| Categorization item | Categories | Reference |
|--|--|---------------------|
| Age | [<65 years, ≥65 years] | <65 years |
| Diagnostic name 1 | [anaerobic infection, infectious enterocolitis] | anaerobic infection |
| Diagnostic name 2 | [anaerobic infection, amebic dysentery] | anaerobic infection |
| Diagnostic name 3 | [anaerobic infection, anaerobic infection plus infectious enterocolitis] | anaerobic infection |
| Hepatic dysfunction | [absent, present] | absent |
| Renal dysfunction | [absent, present] | absent |
| Prior treatment (medication for infection) | [absent, present] | absent |
| Concomitant medications (medication for infection) | [absent, present] | absent |
| Number of daily Anaemetro doses (1) | [1 time, 3 times] | 3 times |
| Number of daily Anaemetro doses (2) | [2 times, 3 times] | 3 times |
| Number of daily Anaemetro doses (3) | [3 times, 4 times] | 3 times |
| Number of daily Anaemetro doses (4) | [3 times, >4 times] | 3 times |
| Dose escalation | [absent, present] | absent |

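### Removing 'inconsistent' patients biases the optional combined-diagnosis contrast for clinical response away from a risk ratio of 1, unless response is 50% or a patient's ratings always agree

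*SAP*

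**What the plan says.** SAP 6.2.1 allows one rating per diagnosis: "In this Study, clinical response may be evaluated for each diagnosis". The condition for the label 'inconsistent' is "If the same patient have multiple diagnoses under investigation with different clinical response", and the reason given is that an overall judgement is then difficult. SAP 8.2.4.1 states the consequence: "the response rate will be calculated by subtracting those patients from the denominator, as in the case where the set includes “indeterminate” patients". That sentence follows the response-rate formula and the by-diagnosis tabulations, and it is not limited to the overall rate. The formula in Protocol 7.7 takes out only 'indeterminate'.

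SAP 8.2.4.4 provides that, for each factor in Section 5.4, "subgroup analysis on clinical response and microbiological response will be performed based on risk ratio and risk difference". Diagnosis is one of those factors. Section 5.4 says that categories for patients with several diagnoses may be added. Appendix 2, headed as an example, lists such a contrast as Diagnostic name 3: "anaerobic infection, anaerobic infection plus infectious enterocolitis", with anaerobic infection as the reference. SAP 8.1.3 attaches 95% confidence intervals to the risk ratio and risk difference but names no method for them. SAP 4.1 treats all tests as exploratory.

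**The concern.** A risk ratio between diagnosis groups is read against a null of equal response. That reading requires the rate to mean the same thing in both groups. Here a patient with two study diagnoses stays in the rate only if both ratings are the same, while a patient with anaerobic infection alone faces no such condition. The exclusion depends on the outcome and falls essentially on one side.

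A reader of the final report could therefore see better (or worse) response in patients with two infections when the exclusion rule alone produced the difference. The row could not show whether a second diagnosis changes response to the drug.

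**Working it through.** **The plan's own figures.** The documents give no figure for this contrast. The only sizing figure is for safety (Protocol 7.5): with 100 patients and a true incidence of 3%, the chance of at least one case is 1 − 0.97^100 = 0.952, which agrees with the stated 95%. It does not bear on the clinical-response contrast.

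**Inputs.** From the SAP: who can be inconsistent (6.2.1), their removal from the denominator (8.2.4.1), the effect measures (8.2.4.4) and the contrast with its reference (5.4, Appendix 2). Assumed, because the documents give neither: a common probability p that any one diagnosis is rated effective, in every patient, and a within-patient correlation ρ between the two ratings.

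**Formulas.**

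- Both effective: A = p² + ρp(1−p)
- Both not effective: B = (1−p)² + ρp(1−p)
- Share of combined-group patients dropped: 1 − A − B = 2p(1−p)(1−ρ)
- Combined-group rate under the plan: A/(A+B)
- Reference rate: p
- Null risk difference: A/(A+B) − p = p(1−p)(1−ρ)(2p−1)/(A+B)

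The last line fixes the direction. The difference is positive for p above 0.5, negative for p below 0.5, and zero at p = 0.5 or ρ = 1 (and trivially at 0% or 100%).

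**Results at p = 0.80**, where the true risk ratio is 1.00:

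| ρ | A | B | Dropped | Combined rate | Risk ratio | Risk difference |
|---|---|---|---|---|---|---|
| 0 | 0.640 | 0.040 | 32.0% | 94.1% | 1.18 | +14.1 points |
| 0.3 | 0.688 | 0.088 | 22.4% | 88.7% | 1.11 | +8.7 points |
| 0.6 | 0.736 | 0.136 | 12.8% | 84.4% | 1.06 | +4.4 points |
| 1 | 0.800 | 0.200 | 0% | 80.0% | 1.00 | 0 |

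**Other response rates.** For ρ = 0, 0.3 and 0.6 the null risk ratio is 1.21, 1.12 and 1.06 at p = 0.70, and 1.10, 1.06 and 1.03 at p = 0.90. At p = 0.40 it is 0.77, 0.87 and 0.94. With equal rates and ρ of zero or more, it cannot exceed about 1.21, reached near p = 0.71 with ρ = 0.

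**Indeterminate ratings.** A simulation with ρ = 0, in which 10% of ratings were indeterminate and a pair with one indeterminate rating counted as different, gave 0.77, 1.00 and 1.18 at p = 0.4, 0.5 and 0.8. The pattern is unchanged.

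**Other ways of scoring the same patients.** Counting them as not effective gives a risk ratio of A/p. At p = 0.80 that is 0.80, 0.86 and 0.92 for ρ = 0, 0.3 and 0.6. Counting them as effective gives (1−B)/p, which is 0.96/0.80 = 1.20 at ρ = 0. Neither is neutral.

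**A neutral comparison.** The anaerobic-infection rating of a patient with both diagnoses has probability p, as it does in a patient with that diagnosis alone, so the ratio is 1. The same simulation gave 1.002, 1.001 and 0.999 at p = 0.4, 0.5 and 0.8.

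**The case against.** **The contrast is not firmly planned.** Section 5.4 says combined categories may be added. Appendix 2 is an example, and it includes dose escalation, which Section 5.4 lists only for safety, so the table is shared with the safety analysis. The further calculations in 8.2.4.4 name three single diseases. This stands: the point applies only if the combined category is analysed for clinical response. The row is nonetheless named, with a reference, and diagnosis is an effectiveness factor.

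**The exclusion may be meant only for the overall rate.** SAP 6.2.1 justifies it by the difficulty of an overall evaluation, and 8.2.4.4 does not repeat it. That reading is possible. However, 8.2.4.1 sets no such limit and 8.2.4.4 defines no other rate, so an analyst following the text would carry the rule over.

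**The reference group may not be wholly exempt.** If two detailed anaerobic diagnoses in one patient were rated separately, some reference patients could be inconsistent too. The SAP does not settle this, which is why the exclusion is described as falling essentially on one side.

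**Zero correlation is unlikely.** For both diseases, an effective rating requires that no other antibacterial treatment is needed afterwards. Read literally, that is a shared condition which makes ratings agree. As an assumed illustration at p = 0.80, if half of the failures come from that shared condition, A = 0.64/0.90 = 0.711, ρ = 0.44 and the risk ratio is 1.08. If three-quarters do, A = 0.64/0.85 = 0.753, ρ = 0.71 and it is 1.04. This stands and favours the lower end of the range.

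**Two stronger readings a reader might infer.** One is that the ratio always exceeds 1. It does not: the direction needs response above 50% and imperfect agreement, and the documents state no response rate. If the two diseases also respond differently, direction depends on both. With independent ratings and 80% for anaerobic infection, the ratio is 0.32/(0.32+0.12)/0.80 = 0.91 when enterocolitis response is 40%, and 1.00 when it is 50%.

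The other is that the plan would often produce a falsely significant result. That depends on an assumed group size and an interval method that the SAP does not name. With 20 combined and 70 single-diagnosis patients, p = 0.80 and ρ = 0, a log-Wald interval excludes 1 in about 52% of simulations, but about 44 of those 52 points come from data in which every retained combined patient responds. A score test gives about 12%, and with 10 combined and 80 single-diagnosis patients 2% or less. No such rate can be attributed to this plan.

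**Little rests on it.** Tests are exploratory, SAP 4.2 sets no decision rules, and the comparison of two diagnoses with one is not a study objective. The listing of clinical responses should also let a reader trace the excluded patients. This lowers the importance but does not make the row interpretable.

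**Conclusion.** The point holds in a conditional form. If the optional combined category is analysed for clinical response with the 8.2.4.1 denominator, the risk ratio and risk difference compare response given agreement with unconditional response. Under identical per-diagnosis response, the result departs from the null unless response is 50% or the ratings always agree.

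The size rests on assumed values. At 80% response and correlations up to 0.6, the null risk ratio lies between about 1.06 and 1.18, with values towards the lower end more plausible. The number of patients with two diagnoses is not stated; if they are few, the row will also be imprecise. The documents do not support a claim that the ratio must exceed 1, or any particular false-positive rate. For an exploratory contrast, the importance is minor to moderate.

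**What to change.** In SAP 8.2.4.4 and Appendix 2, define the clinical-response contrast for combined diagnoses on the disease-specific rating. Compare the anaerobic-infection rating in patients with both diagnoses with the anaerobic-infection rating in patients who have that diagnosis alone, and do the same for the enterocolitis rating. Only a rating of 'indeterminate' for that disease leaves the denominator. In SAP 8.2.4.1, state that the 'inconsistent' exclusion applies to the overall patient-level rate only.

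The cost is about two sentences of SAP text and one changed derivation. No new data are needed: the version 2.0 entry in the SAP's amendment table says that response is collected per clinical diagnosis. The small downside is that two disease-specific comparisons replace one row.
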